15 APR 2016

Page 43 of 137

Trial Protocol Proprietary confidential information © 2016 Boehringer Ingelheim International GmbH or one or more of its affiliated companies

function testing may be postponed up to 14 days to meet this restriction. Subsequent visits will be scheduled according to the patient's regular schedule.

- Temporary additions of the ophylline preparations are allowed during the treatment portion of the study. Pulmonary function testing should not occur within seven days of the last dose. Pulmonary function testing may be postponed up to 14 days to accommodate this restriction. Subsequent visits will be scheduled according to the patient's regular schedule.
- The use of antibiotics is not restricted and may be prescribed as medically necessary for exacerbations and / or infections. If antibiotics are prescribed for a respiratory infection prior to pulmonary function testing days, the testing will be postponed for at least two days but not more than seven days after the last dose is given. Subsequent visits will be scheduled according to the patient's regular schedule.

c03207491-01 Trial Protocol Page 44 of 137

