Concomitant therapy		X	X	X	X	X	$X^3$	X
Medication wash-out		X	X	X	X	X	X	

Boehringer Ingelheim 15 APR 2016

BI Trial No.: 1237.28

c03207491-01 Trial Protocol Page 9 of 137

Proprietary confidential information © 2016 Boehringer Ingelheim International GmbH or one or more of its affiliated companies

		Screening				Treatment Period1		
Visit	0	1	2	3	4, 7	5, 8	6, 9 (V9- EOT)	10
Week of treatment	1	1	-	-	0	3	6	V9-EOT + 3 weeks
Day of treatment Time Window (days)	-	-21 to -14	-13 to -9	-8 to -1	1	22 +7	43 + 7	V9-EOT + 21 + 7
Rescue Medication Use		X	X	X	X	X	$X^3$	
Trial Medication Adherence 						X	$X^3$	
Telephone contacts 		X	X	X	X	X	X	
Trial medication termination							X  (call IRT at V9 only)	
Trial completion								X

- 1. Treatment Period: In this cross-over design, each treatment period (period 1, period 2) will follow the same flow chart:
  - procedures during visits 4 and 7 will be identical (except for inclusion/exclusion check, randomisation and BDI at V4 only)
  - procedures during visits 5 and 8 will be identical
  - procedures during visits 6 and 9 will be identical
- 2. Informed Consent: All patients must sign an informed consent consistent with ICH-GCP guidelines prior to participation in the trial, which includes medication washout and restrictions.
- 3. Procedures: To be completed at the end of each treatment period and / or by all patients who took at least one dose of trial medication including those who discontinue early. PFTs are to be performed if possible.
- 4. Pregnancy Testing: Women of child-bearing potential: serum pregnancy test at visit 1; urine pregnancy test at visits 4, 6, 7, 9, 10.
- 5. ECG: 12-lead ECG recording at screening (visit 1) and end of treatment periods (visits 6 and 9) to be measured pre-dose.
- 6. Body Plethysmography: Conducted prior to dosing with salbutamol for inclusion.
- 7. Device Training: The patient will be instructed in the use of the Respirat® inhaler, but the patient **should not** inhale from the placebo inhaler at these visits.
- 8. Rescue Medication: To be supplied to all patients starting at visit 0.
- 9. Trial Medication Collection: Last dose of trial medication for the respective treatment period will be the morning dose, taken in the clinic on Day 43. All medication is collected after this dosing.

Boehringer Ingelheim BI Trial No.: 1237.28

c03207491-01

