#### Rescheduling after randomisation

Subsequent visits should always be planned to take place to assure a minimum 6 week treatment period and a minimum 3 week wash-out period between treatment periods.

If rescheduling of visits after randomisation is necessary, the total daily doses of the Respimat® inhaler need to be obeyed. Reserve medication is dispensed at each treatment period to avoid intermediate visits.

If rescue medication is administered during a visit day within 8 hours prior to administration of trial medication, the visit will be rescheduled once. Further rescheduling should be discussed with the CML.

Refer to sections 4.2.1 and 4.2.2 for details on medications allowed to control acute COPD exacerbations and restrictions for these medications prior to PFTs.

In case a visit needs to be rescheduled outside the allowed time window (e.g. in order to meet PFT wash-out requirements following treatment of an acute exacerbation), the CML should be contacted.

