### Patient baseline

The patient baseline is defined as the mean of non-missing period baselines for each patient.

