6. GENERAL ANALYSIS DEFINITIONS

6.1 TREATMENTS

The doses to be administered are described in Section 4 of the CTP.

This is a crossover trial consisting of a 3 to 4-week run-in period followed by two six-week treatment periods and a three-week post-treatment period. The day after the follow-up visit will be considered the start of the post-study period in case there are any subsequent AE data we become aware of. There will be 3-week washout between treatment periods.

For the main safety analysis, data occurring during the treatment periods and within 21 days of stop of study drug for the period will be assigned to the respective treatment for that period. Data occurring before the first drug intake date is assigned to “screening”. If the next treatment period starts within 21 days of the end of the last period, data after the start of treatment for the next period will be assigned to the treatment for that period. Data more than 21 days after drug stop date for a period but before the start of the next period will be assigned to washout. Data more than 21 days after the end of the last treatment period and up to and including the date of the study termination will be assigned to post-treatment. Data after study termination will be assigned to post-study.

Any cases of patient being treated with the wrong study medication will be identified and summarised as an important protocol violation (PV).

- If a patient was treated with a treatment sequence different from the randomised treatment sequence throughout the on-treatment period, i.e., a patient was treated with incorrect study medication during every treatment period, this patient will be included in the treated set and will be analysed as treated for both efficacy and safety analyses, including patient disposition. Such a case will be reported as an important PV and this patient will be excluded from the per-protocol set (PPS).

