Table 6.2: 1 Important protocol violations

Category / Code	Description	Requirements	Excluded from	Automatic/ Manual
A	Entrance criteria not met			
	A1	Inclusion criteria not met	Inclusion Criteria 2-9 not met as specified in the protocol.	Exclude from PPS*: 2-9
	A2	Exclusion criteria not met	Exclusion Criteria 1-30 not met as specified in the protocol	Exclude from PPS*: 3, 4, 8-12, 14-25, 29, 30
B	Informed consent			
	B1	Informed consent not available/not done	Informed consent date missing; no signature on ICF.	All
	B2	Informed consent too late	Date of informed consent was after the date of any study-related procedure, or a patient signed the correct version of the ICF after Visit 0. If date of informed consent equals to date of Visit 1, such cases will be discussed at MQRM/BRPM/DBL meetings.	None
C	Trial medication and randomisation			
	C1	Incorrect trial medication taken	Not throughout study; could be at a clinic visit or between clinic visits. External vendor will check before unblinding.	PPS (decision at BRPM)
	C2	Randomisation order not followed	Throughout the study	PPS
	C3	Non-compliance with study medication		
	C3.1	Serious non-compliance with study medication as reported in monitoring report or manual PV spreadsheet	Decision at BRPM/MQRM.	PPS if at Visit 6 or 9
	C4	Medication code broken inappropriately	To be discussed and decided during MQRM/BRPM. Only inappropriate code breaks are IPVs (e.g. unblinding by Global Pharmacovigilance is not).	PPS

Table 6.2: 1 (continued) Important protocol violations

Category / Code		Description	Example/Comment	Excluded from	Automatic/ Manual
D		Concomitant medication			
	D1	Improper medication washout at baseline visit or primary endpoint visit(s)	Visit 4,6,7,9. Decision at BRPM	PPS	Automatic and Manual
	D2	Prohibited medication use during study	Check CT. Decision at BRPM.	PPS if in the week prior to Visit 4,6,7,9	Automatic and Manual
F		Incorrect timing			
	F3	Primary endpoint recorded outside time window			
	F3.5	Constant speed shuttle test <1 hour or >3 hours after inhalation	Only at Visits 6, 9	PPS	Automatic
Z		Other			
	Z1	Serious GCP non-compliance	Manual PVs reported by CML/CRA which are considered as important. Carefully reviewed, described and documented in DBL meeting minutes.	PPS	Manual

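### Could following the 'regular schedule' after a postponed visit 6 shorten the washout and distort the primary comparison?

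*Protocol*

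**What the plan says.** Protocol 4.2.1 lists what may be given for an acute exacerbation. When oral steroids are added or increased, the rule for lung testing reads in part: "function testing may be postponed up to 14 days to meet this restriction. Subsequent visits will be scheduled according to the patient's regular schedule". The theophylline item has the same 14-day allowance, and the antibiotic item has a shorter one (two to seven days after the last dose). All three return the patient to a regular schedule that the section does not define.

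Protocol 6.1, under rescheduling after randomisation, says later visits should always be planned "to assure a minimum 6 week treatment period and a minimum 3 week wash-out period between treatment periods". It refers back to 4.2.1 for the medication restrictions. It also names a visit pushed out of window by exacerbation treatment as a case for contacting the local monitor. The general part of 6.1 requires deviations from the visit schedule to be documented.

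Flow chart footnote 1 begins "In this cross-over design, each treatment period (period 1, period 2) will follow the same" and goes on to refer to one chart, whose days are counted from day 1 of the period. Footnote 9 says: "Last dose of trial medication for the respective treatment period will be the morning dose, taken in the clinic on Day 43".

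In Protocol 7.3.1 the pre-dose visit 7 test gives the period 2 baseline, and "The patient baseline is defined as the mean of non-missing period baselines for each patient".

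In SAP Table 6.2:1 the timing code F3.5 reads "Constant speed shuttle test <1 hour or >3 hours after inhalation". D1 covers faulty medication washout at visits 4, 6, 7 and 9, and Z2 is a catch-all for other violations affecting efficacy. Both are checked automatically and manually. SAP 6.1 has a clause beginning "If the next treatment period starts within 21 days of the end of the last period", used to assign safety data. SAP Table 6.7:1 derives actual study days from both period start and study start.

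**The concern.** The planned calendar has no slack: visit 6 is day 43, visit 7 is day 64, and the difference is exactly the three-week minimum. Footnote 9 ties the last period 1 dose to the end-of-period visit. If that visit slips and visit 7 stays on its original date, the delay comes out of the washout.

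The visit 7 test would then be done with less time off the period 1 drug, and its value enters both baseline covariates of the primary model. The patients concerned would have been treated for an exacerbation or infection, so they are not a random subset. If the SAP had no way to identify them, the reader of the report could not tell how many there were or whether they mattered.

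**Working it through.** **Inputs.** Planned days 43, 64 and 106 for visits 6, 7 and 9 (SAP Table 6.7:1). Postponement up to 14 days (Protocol 4.2.1). Visit 6 and 9 window of +7 days (flow chart). Minima of 42 and 21 days (Protocol 6.1). Difference 0.5, SD 1.776, two-sided alpha 0.05, n = 102 (Protocol 7.7).

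**1. The plan's own figures.** A one-sample t-test with these inputs needs n = 101 for 80% power (0.8001) and n = 135 for 90% (0.901), as stated. At n = 102 power is 0.804. Planned washout is 64 − 43 = 21 days and planned period 2 is 106 − 64 = 42 days.

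**2. The two readings of 4.2.1.**

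| Visit 6 on day | Washout if visit 7 stays on day 64 | Visit 7 if counted per period | Washout |
|---|---|---|---|
| 43 | 21 | 64 | 21 |
| 50 (+7) | 14 | 71 | 21 |
| 57 (+14) | 7 | 78 | 21 |

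**3. Which reading fits the other passages.** With visit 7 fixed on day 64, even a visit 6 on day 50, inside its permitted window, would leave 14 days and miss the minimum in 6.1. The calendar reading therefore puts the flow chart's ordinary window in conflict with 6.1. The per-period reading leaves 4.2.1, 6.1 and the flow chart in agreement.

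**4. A short treatment period.** Section 4.2.1 only postpones testing, and the visit 6 and 9 window runs forward only, so an early test is already out of window. A 28-day period 2 (106 − 78) needs visit 7 itself to be postponed 14 days while visit 9 stays on day 106. The 4.2.1 list is written for the treatment period, so it is not clear that it covers visit 7.

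**5. Size if the calendar reading were followed.** The patient baseline is the same in both periods, so it cancels from the within-patient contrast; only the period baseline matters. Suppose k of 102 patients, split evenly over the sequences, carry a residual treatment difference r at visit 7, and the within-patient baseline slope is b. The contrast moves by b × (k/102) × (r/2). None of b, k or r is in the documents; the ranges below are assumptions. With r = 0.5, the whole planned effect:

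- k = 5: 0.3 × 0.0490 × 0.25 = 0.004, up to 0.8 × 0.0490 × 0.25 = 0.010.
- k = 10: 0.3 × 0.0980 × 0.25 = 0.007, up to 0.8 × 0.0980 × 0.25 = 0.020.

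The largest value is 0.0196/0.5 = 3.9% of the planned difference, towards a larger apparent benefit of the combination. The standard error is 1.776/√102 = 0.176, so it is about 0.11 standard errors. If only 10 to 50% of the effect persisted, the range is 0.0004 to 0.010.

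**6. The opposite assumption.** Suppose instead that a fraction c of the 0.5-unit effect carries into the period 2 outcome in a share f of patients. The estimate then shrinks by 0.5 × c × f/2. For f from 5 to 20% and c from 10 to 50%, that is 0.001 to 0.025 units, with power at n = 102 between 0.80 and 0.76. The upper end is severe: with visit 6 on day 57 and visit 9 on day 106, the outcome is measured 106 − 57 = 49 days after the last period 1 dose.

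**The case for a change.** The best argument for acting is that the SAP gap does not depend on how 4.2.1 is read. Whatever the cause of a short interval, no visible code states a number of days. F3.5 concerns hours, the full analysis set has no duration condition, and the under-21-day clause in SAP 6.1 serves safety only. D1 does not say whether it covers trial-drug washout or only other medication, and it is settled at the blinded meeting. The supportive per-protocol analysis runs only if that set falls below 90% of the full analysis set, and ten exclusions leave 92/102 = 90.2%. A programmed flag would be cheap and would replace judgement with a rule.

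Part of this stands. The term in 4.2.1 is undefined, that section does not point to the minima, D1's scope is not spelled out, and no tabulation of short intervals is pre-specified in the visible text.

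The rest does not carry the weight put on it. D1 names visit 7 and, like Z2, includes an automatic check. Deviations from the visit schedule are documented, and the actual days of visits 6 and 7 are in the analysis data sets, so the interval can be computed and discussed before unblinding. Parts of SAP 6.6 and 6.7 are redacted, so absence can be asserted only for what is visible. The 90% trigger is a general rule and not a fault in washout handling. An extra analysis without the affected patients would guard against a shift of a few hundredths of a unit at most, and dropping ten patients would lower its power to 76.2%.

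**Conclusion.** No change to the plan. Sections 4.2.1 and 6.1 conflict only if a phrase in the first is read as fixed calendar dates and the explicit minima in the second are set aside. With the minima kept, the washout remains 21 days and the primary analysis is unaffected. Should a site be found working from fixed dates, the sponsor would have to reconcile the two sections; this note does not choose the scheduling rule.

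Under the calendar reading, the shift in the primary contrast is at most 0.020 Borg units through the visit 7 baseline, or 0.025 in the other direction under outcome carry-over, against a planned difference of 0.5. Even the sign depends on the assumption. These figures rest on assumed numbers of affected patients, residual effects and baseline slopes, set mostly at the pessimistic end. What remains is a missing definition and a criterion left to the blinded review, which analysts can fill from variables already derived. The sample size, the primary model and the analysis sets stand as written.

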## Proprietary confidential information © 2016 Boehringer Ingelheim International GmbH or one or more of its affiliated companies

## 4.2.2 Restrictions

Table 4.2.2:1 Restrictions regarding concomitant treatment

			Study Period			
Drug Class	Sub-class	Prior to study	Screening Period	Treatment Period	Wash-out Period	Follow up Period
Corticosteroids	Inhaled corticosteroids (stabilized 4 wks prior to V1)	Permitted 1&5	Permitted 1&5	Permitted 1&	Permitted 1&	Permitted 1&5
	Oral corticosteroids [≤10 mg prednisone per day or ≤20 mg prednisone every other day (or equivalent); stabilized 4 wks prior to V1]	Permitted	Permitted	Permitted	Permitted	Permitted
	Injected Corticosteroids – local administration (for treatment of e.g. bursitis)	Permitted	Permitted	Permitted	Permitted	Permitted
	Nasal Corticosteroid sprays	Permitted 	Permitted 	Permitted 	Permitted 	Permitted 
β-adrenergics	Inhaled short-acting β- adrenergics	Permitted 	Rescue 	Rescue 	Rescue 	Permitted
	Inhaled long-acting β-adrenergics (bid) (e.g. formoterol / salmeterol)	Permitted  (w.o. 48 hrs prior to V1)	NOT permitted	NOT permitted	NOT permitted	Permitted
	Inhaled long-acting β-adrenergics (qd) (i.e. indacaterol, olodaterol)	Permitted  (w.o.1 wk prior to V1)	NOT permitted (w.o.3wks prior to V4)	NOT permitted	NOT permitted	Permitted

c03207491-01 Trial Protocol Page 45 of 137

Proprietary confidential information © 2016 Boehringer Ingelheim International GmbH or one or more of its affiliated companies

		Study Period				
Drug Class	Sub-class	Prior to study	Screening Period	Treatment Period	Wash-out Period	Follow up Period
	Oral and patch beta-adrenergics	NOT permitted 	NOT permitted	NOT permitted	NOT permitted	NOT permitted
	Beta blockers (stabilized 6 wks prior to V1)	Permitted	Permitted	Permitted	Permitted	Permitted
Anti-cholinergics	Short-acting anticholinergics (inhalation aerosol, nasal spray)	Permitted 	Permitted  (w.o. 8 hrs prior to V2, V3,V4)	NOT permitted	Permitted  (w.o. 8 hrs prior to V7)	Permitted
	Long-acting anticholinergics (bid/qd) (i.e. tiotropium, aclidinium, glycopryonnium, umeclidinium)	Permitted (w.o. 1 wk prior to V1)	NOT permitted (3 wks prior to V4)	Study medication	NOT permitted	Permitted
Combinations	ICS/LABA (bid) (* switch to ICS mono-product, at the same or equivalent dose, at least 48 hrs prior to V1)	Permitted 	NOT permitted*	NOT permitted	NOT permitted	Permitted
	ICS/LABA (qd) (*switch to ICS mono-product, at the same or equivalent dose, at least 1 wk prior to V1) (e.g. fluticasone +vilanterol)	Permitted	NOT permitted*	NOT permitted	NOT permitted	Permitted
	ICS/SABA  (* switch to ICS mono-product, at the same or equivalent dose, at least 8 hrs prior to V1)	Permitted 	NOT permitted*	NOT permitted	NOT permitted	Permitted
	short-acting anticholinergic/ SABA (* 8 hrs prior to V1)	Permitted 	NOT permitted*	NOT permitted	NOT permitted	Permitted

c03207491-01 Trial Protocol Page 46 of 137

Proprietary confidential information © 2016 Boehringer Ingelheim International GmbH or one or more of its affiliated companies

			Study Period			
Drug Class	Sub-class	Prior to study	Screening Period	Treatment Period	Wash-out Period	Follow up Period
	Long-acting anticholinergics/long- acting β-adrenergics²(e.g. glycopyrronium+indacaterol, umeclidinium+vilanterol)	Permitted (w.o. 1 week prior to V1)	NOT permitted (w.o. 3 wks prior to V4)	Study medication	NOT permitted	Permitted
Antibiotics	For respiratory infections The use of antibiotics is not restricted and may be prescribed as medically necessary for COPD exacerbation episodes and / or infections.	Permitted (w.o. 4 wks prior to V1)	Permitted (except antibiotics for prevention of exacerbation of COPD)		n of COPD)	
	Any other infections	Permitted (w.o. 4 wks prior to V1)	Permitted	Permitted	Permitted	Permitted
Miscellaneous	Other investigational drugs (* 1 mth or 6 half-lives (whichever is greater) prior to V1)	NOT permitted*	NOT permitted	NOT permitted	NOT permitted	NOT permitted
	Cromolyn sodium / nedocromil sodium 	Permitted	Permitted	Permitted	Permitted	Permitted
	Antihistamines (including nasal route), antileukotrienes 	Permitted	Permitted	Permitted	Permitted	Permitted
	Methylxanthines 	Permitted 	Permitted 	Permitted 	Permitted 	Permitted 
	Mucolytics (not containing bronchodilators; stabilized 4 wks prior to V1)	Permitted	Permitted	Permitted	Permitted	Permitted
	Mucolytics containing bronchodilators	NOT permitted 	NOT permitted	NOT permitted	NOT permitted	NOT permitted
	Phosphodiesterase type 4 (PDE4) inhibitor  (e.g. roflumilast)	NOT permitted	NOT permitted	NOT permitted	NOT permitted	NOT permitted

Boehringer Ingelheim
15 APR 2016
BI Trial No.: 1237.28

c03207491-01 Trial Protocol Page 47 of 137

Proprietary confidential information © 2016 Boehringer Ingelheim International GmbH or one or more of its affiliated companies

- 1 Refer to section 4.2.2.1 for washout period prior to PFTs.
- 2 Patients may be switched to bid LABA and short acting anticholinergic. Refer to section 4.2.2.1 for washout period prior to PFTs.
- 3 For the ophyllines: Refer to section 4.2.2.1 for washout period prior to PFTs.
- 4 Patients currently using PDE4-inhibitors (e.g. roflumilast) should not be enrolled and roflumilast should not be withdrawn for the purpose of enrolling in this study. Patients who were using roflumilast in the past may be included if their last use was a minimum of 3 months prior to visit 1. In the event a patient with prior use of roflumilast is enrolled, past medical records are required to support and document why and when roflumilast was stopped.
- 5 Permitted if prescribed for non-asthma condition
- 6 Not permitted within 4 weeks prior to screening visit (w.o. 4 wks prior to V1)

Refer to section 4.2.1 for washout period prior to PFTs in case of treatment of a COPD exacerbation

#### 4.2.2.1 Restrictions for PFT and shuttle tests

- At least an 8-hour washout of short-acting beta-adrenergic bronchodilators.
- At least an 8-hour washout of short-acting anticholinergic bronchodilators prior to visits 1, 2, 3 and 4 (Not allowed during treatment periods but permitted during the wash-out period, with at least an 8-hour washout prior to V7).
- At least a 1-week washout of long-acting anticholinergic bronchodilators twice daily (bid) or once daily (qd) prior to visit 1 and a 3-week washout prior to visit 4. (Not allowed between visits 1 to 9).
- At least a 1-week washout of long-acting beta-adrenergic bronchodilators (qd) prior to visit 1 and a 3-week washout prior to visit 4 (Not allowed between visits 1 to 9).
- At least a 48-hour washout of long-acting beta-adrenergic bronchodilators (bid) prior to visit 1 (Not allowed between visits 1 to 9).
- The morning dose of inhaled steroids should not be taken in the 1-hour period prior to PFTs.
- Morning doses of study medication should not be taken prior to test-day pre-dose PFT.
- At least a 24-hour washout of short-acting (bid or more frequent administration) theophylline preparations.
- At least a 48-hour washout of long-acting (qd administration) theophylline preparation.

A patient visit may be re-scheduled twice due to lack of medication washout compliance. After this, a discussion with the Clinical Monitor should take place regarding the patient continuing in the trial

